A comparison of Mepitel Ag vs antibiotic ointment when used with a soft cast technique for the treatment of pediatric hand and foot burns, a prospective study

Protocol #: 15-1828

April 8, 2016

COMIRB Protocol

COLORADO MULTIPLE INSTITUTIONAL REVIEWBOARD
[name] [contact] [contact]

Protocol #: 15-1828

Project Title: A comparison of Mepitel Ag vs antibiotic ointment when used with a soft cast technique for the treatment of pediatric hand and foot burns, a prospective study

Principal Investigator: [name], MD

Version Date: 3/30/16

- I. **Hypotheses:** Mepitel Ag in combination with the soft cast technique improves wound healing in pediatric partial to deep partial thickness hand and foot burns by decreasing the length of healing time, decreasing the risk of yeast infection, and decreasing pain associated with multiple dressing changes.
- II. **Specific Aims:**
 - 1) To examine the efficacy of Mepitel Ag for use in pediatric partial to deep partial thickness hand and foot burns.
 - 2) To evaluate Mepitel Ag to triple antibiotic ointment when used in combination with a soft cast technique comparing healing time, yeast infection rates and pain levels at time of dressing change.

II. Background and Significance:

There is currently no gold standard dressing when it comes to treating hand or foot burns, specifically in the pediatric population. Our institution currently utilizes a soft cast technique (SCT) on all of our hand and foot burns. The SCT provides optimal positioning of the wounded hand or foot, allows for a moist wound environment, and offers protection of the injured extremity as the wound heals. Our current SCT uses triple antibiotic ointment (TAO) impregnated Adaptic gauze, kling or kerlex, cast padding, gypsoma plaster, soft cast material, and coban. This dressing is applied two to three times during the first 2 weeks post injury. To reduce the risk of the development of yeast overgrowth, the underlying dressing is changed to nystatin impregnated Adaptic gauze, kling or kerlex, cast padding, gypsoma plaster, soft cast material, and coban for the remainder of treatment time or until OR is indicated for surgical debridement and grafting of wounds..

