A review of the current literature demonstrates silver sulfadiazine (SSD) to be the most frequently used dressing for burn wound treatment in many clinics nationwide.²⁸ The use of SSD is associated with once to twice daily painful dressing changes and wound exposure that "may lead to disruption of newly formed epithelium, wound colonization, subsequent wound infection and deepening of the burn".^{23, 28} One major benefit of the SCT is the reduction in

required dressing changes, as the soft cast can stay in place for 7-10 days while maintaining optimal hand or foot positioning. This eliminates the need for frequent painful dressing changes.

Occasionally, We have observed yeast infections when patients require serial casting and all have been treated with antibiotics. Other complications we have experienced include: occasional drying out of the adaptic gauze leading to a painful dressing removal and interruption of the newly epithelialized wound bed.

Mepitel Ag, a new soft silicone dressing produced by Molnlycke Health Care, combines Safetac technology with a silver compound to provide a broad spectrum of antimicrobial coverage. The safetac technology “protects the wound and the skin. It prevents an outer dressing from sticking to the wound, therefore minimizes trauma and pain”.¹⁵ The highly pliable nature and antimicrobial properties of the dressing make it an ideal alternative to TAO and SSD for the treatment of pediatric partial to deep partial thickness hand and foot burns. The silver compound lasts up to 8 days, while minimizing damage to the new epithelium and creating a moist wound environment. As Mepitel Ag is a relatively new product, there are currently no studies analyzing its efficacy and effectiveness when compared to other burn treatment methods.

The aim of this study is to compare Mepitel Ag to triple antibiotic ointment impregnated Adaptic gauze when used with the soft cast technique to assess overall time to healing, yeast infection rate and parents perception of pain level at time of dressing change on a scale of 1-10. The hypothesis is that Mepitel Ag in combination with the soft cast technique improves wound healing in pediatric partial to deep partial thickness hand and foot burns by decreasing the length of healing time, decreasing the risk of yeast infection, and decreasing pain associated with dressing changes.

III. Preliminary Studies/Progress Report:

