New burn clinic patients identified with a partial to deep partial or full thickness hand or foot burn will be randomized into either the Mepitel Ag group or the control group on their first clinic visit based on burn wound severity and age using RedCap. The randomization scheme in RedCap will be independently created by a statistician. Parental consent and or patient assent will be obtained prior to initial dressing. Burn severity will be clinically determined by one provider and one burn nurse during initial exam based on a 10 point burn severity classification scale in regards to the following parameters: 1) Superficial first degree- wound appears pink or red, involves epidermis only, no blisters present, dry; 2) Second degree, superficial partial thickness- burn involves epidermis + dermis, red or bright pink in color with blisters and or swelling, blanches, moist appearing; 3) Second degree, majority superficial partial thickness, minority superficial- burn involves majority ($\geq 66\%$) superficial partial thickness, epidermis + dermis, red or bright pink in color with blisters and or swelling, blanches, moist appearing, minority ($\sim 33\%$ or less) superficial first degree with areas of redness but no blistering; 4) Second degree, majority partial thickness, minority deep partial thickness- majority of burn ($\geq 66\%$) epidermis + dermis, red or bright pink in color, moist, less than half of burn ($\sim 33\%$ or less) is deep with pale pink-white areas, may or may not have a marbled or mosaic appearance; 5) Second degree, deep partial thickness- involves epidermis + dermis, pale pink to white in color, may have thin white moist eschar, may or may not have a marbled or mosaic type appearance, moist; 6) Second degree, majority deep partial thickness, minority superficial partial thickness- minority of burn ($\sim 33\%$ or less) involves epidermis + dermis, red or bright pink in color, moist, majority ($\geq 66\%$) of burn is deep with pale pink-white areas having a marbled or mosaic appearance, may or may not have thin white moist eschar, skin buds may or may not be present; 7) Second degree, deep partial thickness with areas of full thickness- majority of burn ($\geq 66\%$) involves epidermis + dermis, pale pink to white in color, may have thin white moist eschar, may or may not have a marbled or mosaic type appearance, moist, skin buds may or may not be present, minority of burn ($\sim 33\%$ or less) demonstrates thin to thick area of eschar white, brown or black in color, may need skin graft to heal; 8) Third degree full thickness with minority partial thickness- majority of burn ($\geq 66\%$) involves entire dermis + epidermis, thin to thick eschar that is white, brown or black in color, dry appearing, minority of burn ($\sim 33\%$ or less) is pink or red and moist, with blisters and or swelling, blanches; 9) Third degree full thickness- involves entire dermis + epidermis, thin to thick eschar that is white,

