Analysis Plan: Demographic and clinical characteristics will be summarized and compared between the two treatment groups using chi-squared and two-sample t-tests for categorical and continuous data, respectively. For analysis of the primary outcome, time to wound healing, we will use Kaplan-Meier curves, the log-rank test and a Cox proportional hazards model to determine the difference in days to re-epithelialization between the TAO and Mepitel Ag soft cast methods. Patients that require surgical intervention will be censored at the time of surgery. Logistic regression will be used to analyze the secondary outcomes, need for surgical debridement and occurrence of yeast infection. Pain level outcomes and pain medication use will be compared using two-sample t-tests and chi-squared tests. Cost effectiveness outcomes will also be analyzed.

1. Sample size: A statistical power analysis was performed to estimate power, based on results reported in A Soft casting Technique to Manage Pediatric Hand Burns: Less Pain, Greater Gain.²² Considering the simplest between group comparison and assuming a standard deviation of 0.3, alpha of 0.05 and 50 subjects per group there is over 90% power to detect a difference of 2 days between the treatment groups. Thus, we expect that our proposed sample size of 100 burns will be adequate for the main objective of this study.

G. Summarize Knowledge to be Gained:

To demonstrate that Mepitel Ag in combination with a soft cast technique improves wound healing in pediatric partial to deep partial thickness hand and foot burns by decreasing the length of healing time, decreasing the risk of yeast infection, and decreasing pain associated with dressing changes.

H. References:

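### Healing time has no stated day 0, entry does not bound time since injury, and the Cox model does not adjust for it

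*Combined protocol and SAP*

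**What the plan says.** Section IV.B admits burns that are newly diagnosed, and IV.C adds that "New burn clinic patients identified with a partial to deep partial or full thickness hand or foot burn will be randomized" at the first clinic visit. Neither states a maximum time since injury. The exclusions in IV.B cover silver and silicone allergy but not earlier dressings. Allocation takes account of severity and age (severity alone in a later paragraph of IV.C), not of time since injury.

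Section IV.A measures the primary outcome in days to re-epithelialization. Section IV.F uses Kaplan-Meier curves, the log-rank test and a Cox model "to determine the difference in days to re-epithelialization between the TAO and Mepitel Ag soft cast methods". The one rule it gives for the time variable is censoring at surgery. It names no start of the clock and no covariates. The data items listed in IV.C and IV.D include neither date of injury nor prior dressing, and IV.E does not list burn age among the limitations.

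The sample size paragraph of IV.F claims that "there is over 90% power to detect a difference of 2 days between the treatment groups". Its inputs are an SD of 0.3, a 5% significance level and 50 burns in each arm.

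**The concern.** A survival analysis needs a defined origin. Here day 0 could be the injury, the first clinic visit, randomisation or the first study dressing. The middle two and the last probably fall close together, so the choice that matters is injury or first visit.

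Suppose two children both heal 14 days after injury, one first seen on day 1 and the other on day 7. Counted from injury, both have 14 days. Counted from the visit, they have 14 − 1 = 13 and 14 − 7 = 7 days. That gap of 6 days reflects burn age alone, in a trial planned around a difference of 2 days.

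Because allocation is random, such gaps should fall evenly on both arms. They should not favour either dressing, but they can widen the spread within each arm and make a true difference harder to detect. If date of injury is not recorded, the analysis cannot correct for this afterwards.

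**Working it through.** **Inputs from section IV.F:** difference 2 days, 50 per group, alpha 0.05 (taken as two-sided), SD 0.3 (taken as days). **Assumed, because the documents do not give them:** a credible SD, mean healing time, and spread of entry times.

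**1. The plan's own figure.** Standard error = 0.3 × √(2/50) = 0.06 days, and 2/0.06 = 33.3, so power is about 100%. The stated claim of over 90% holds as an inequality. But an SD of 0.3 does not explain a choice of 50 per group. The largest SD that gives 90% power is 2/[√(2/50) × (1.960 + 1.282)] = 2/(0.2 × 3.242) = 3.08 days. At SD 3 the standard error is 0.6, 2/0.6 = 3.33, and power = Φ(3.33 − 1.96) = 91.5%. I use SD 3 as the main assumption because it fits the stated sample size. The value of 0.3 is a separate matter for the sponsor to check.

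**2. Noise alone.** If entry is uniform over 0 to 7 days, the SD of the lag is 7/√12 = 2.02, about 2 days. If healing time from injury has SD 3 and does not depend on the lag, time from the first visit has SD √(3² + 2²) = 3.61. The standard error is 3.61 × 0.2 = 0.72, 2/0.72 = 2.77, and power = Φ(2.77 − 1.96) = 79%. So, with the full 2-day effect kept, power falls from 91.5% to about 79%.

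**3. Simulation.** Healing time from injury is gamma with mean 14 days; entry lag is uniform; only unhealed burns enter. Mepitel Ag multiplies the remaining time by 12/14. There are 50 independent burns per arm, tested at two-sided 5%. The linear-model runs used 4,000 replicates and the Cox runs 300. Ranges show agreement between repeated runs.

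| Model | SD (days) | Entry spread (days) | Visit clock, unadjusted | Visit clock, adjusted | Injury clock, unadjusted |
|---|---|---|---|---|---|
| Cox | 3 | 0–7 | 64% | 77% | 76% |
| Linear | 3 | 0–7 | 59–61% | 75% | 75% |
| Linear | 4 | 0–7 | 44–45% | 52–54% | 53% |

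With entry within 1 day, linear-model power is 92–93% at SD 3 and 72–73% at SD 4, and the clock and the covariate make almost no difference. With entry over 0 to 3 days it is 86–89% at SD 3 and 64–67% at SD 4.

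**4. Precision.** With 300 runs, the Monte Carlo standard error is √(0.64 × 0.36/300) = 2.8 points at 64% and √(0.77 × 0.23/300) = 2.4 points at 77%. The gap of 77 − 64 = 13 points is real under the model; 77% and 76% cannot be told apart.

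**5. Why adjust, if an unadjusted injury clock does as well?** That result follows from modelling healing as timed from injury. If time from the visit were instead unrelated to burn age, the injury clock would carry the extra variance, by the arithmetic of step 2. In a linear model the two clocks give the same treatment estimate once the lag is a covariate, because they differ only by that lag. The covariate therefore protects under either assumption.

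**The case against.** Several points on the other side stand.

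- **The text leans towards early entry.** Burns are newly diagnosed, consent comes before the initial dressing, and IV.D calls the trial time sensitive. Background says of current practice, "This dressing is applied two to three times during the first 2 weeks post injury", which suggests that the first cast usually comes early. None of this is an eligibility rule, but together it narrows the risk.
- **The lag and SD are assumptions.** An entry spread of 0 to 7 days drives the larger losses; over 0 to 3 days they are modest. At the plan's own SD of 0.3, even halving the effect leaves power near 100%.
- **The gain is over one reading only.** It is measured against an unadjusted clock from the first visit. An unadjusted clock from injury performs as well as the adjusted analysis in the simulated model.
- **Broad entry is a legitimate choice.** IV.B sets out to include all eligible burn patients at the hospital.

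A reader might infer something stronger: that late-referred burns will dilute the 2-day effect. In the simulated model the mean contrast does fall, from about 1.9 days to 1.5, and adjustment cannot restore that. But this treats 2 days as the effect of starting at injury. IV.F states it as a difference between the treatment groups, which may already reflect the clinic's usual referral pattern. The documents do not show how many late burns enter.

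A reader might also infer that earlier silver or antifungal treatment will blur the comparison. Background calls "silver sulfadiazine (SSD) to be the most frequently used dressing for burn wound treatment in many clinics nationwide", which says nothing about this clinic's referrals, and no section mentions antifungal dressings before referral.

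What the objections leave untouched is the missing day 0 and the missing adjustment.

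**Conclusion.** The three omissions are established from the text: no day 0, no bound on time since injury, and no adjustment for it. The first needs no assumption, because the primary analysis cannot be reproduced without an origin.

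The loss of power is conditional. It arises if burns of differing age enter and the clock runs unadjusted from the first visit. At SD 3 days with entry spread over 0 to 7 days, adjustment raises Cox power from about 64% to 77%; with entry within 1 day it changes almost nothing. These figures assume the effect form, mean, SD and independent burns described above. No systematic bias between arms is claimed, and the documents do not support a finding that the planned effect will in fact be diluted. This is an inexpensive improvement to the analysis plan, not a demonstrated failure of power.

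**What to change.** In IV.F, state that healing time is counted in days from randomisation (day 0), and that the primary Cox model includes treatment and days from injury to randomisation as a prespecified covariate. Say also that the primary conclusion rests on this adjusted model, since the log-rank test does not use the covariate. In IV.C, add date of injury and prior dressing to the data recorded at the first visit.

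An entry window or a prior-dressing exclusion is optional. It would trade a narrower population against the plan to enrol all burn patients, and both the decision and any values are for the sponsor.

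The cost is one or two history fields and one model term for 100 burns. If nearly all burns enter early, the covariate does little and costs almost nothing.

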Patients to be included in this study will be all Children's Hospital Colorado burn patients between the ages of 31 days and 18 years with newly diagnosed partial to deep partial or full thickness hand or foot burns, including bilateral or unilateral injury. Each injured extremity will serve as a separate data point. Exclusions include age > 18 years at start of study, silver allergy, silicone allergy, electrical or chemical burn, past medical history of immunodeficiency disorders such as diabetes mellitus, AIDs, or HIV, pregnant women, prisoners children under the protection of the department of human services, and the decisionally challenged.

C. Study Design and Research Methods

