
brown or black in color, dry appearing; 10) Fourth degree- third degree + muscle and or bone involvement. The provider and burn nurse will each give the patient a number and the severity will be determined based on the average of the 2 numbers. Any patient given a number 2, 3 or 4, will be placed into the "partial thickness" category, any patient given a 5, 6, or 7 will be placed into the "deep partial thickness" category, and lastly, any patient given an 8 or 9 will be placed into the "full thickness" category for burn severity.

Patients will be randomized into one of two groups, Mepitel Ag or standard TAO, using RedCap and based on a random clinical trial excel spread sheet balanced by burn severity. A statistician will provide a randomization scheme for investigators to follow. Photographs will be taken prior to dressing application at the initial visit and each subsequent visit. ~~Patient wounds will be dressed in either Mepitel Ag, kling or kerlex, cast padding, gypsoma plaster, soft cast material and coban for up to 21 days or until complete re-epithelialization of the wound occurs or unless surgery is indicated; the control, standard dressing of Triple Antibiotic Ointment impregnated adaptic gauze, kling or kerlex, cast padding, gypsoma plaster, soft cast material and coban for 10-14 days, or Nystatin impregnated adaptic, kling or kerlex, cast padding, gypsoma plaster, soft cast material and coban for 8-21 days or until complete re-epithelialization of the wound occurs or surgery is indicated. The SCT is applied by Occupational and Physical trained in casting and positioning. The soft cast provides optimal positioning while eliminating friction on the burn area. Dressing changes will occur every 3-10 days and will be determined by the provider, based on burn wound severity. Upon each return clinic visit, the patient will have their wound severity assessed by the following scoring system: 1=0% healed, 2=20% healed; 3=40% healed; 4=60% healed; 5=80% healed; 6=100% healed. This will be established by provider and burn nurse examination of the wound. This will be recorded in RedCap:_____~~

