A member of the nursing team will also complete a questionnaire at each follow up visit to indicate pain level with dressing change based on the FLACC scale, parents perceived level of pain during dressing change, parental reported pain level at home, use of home pain medications, type of home pain medication- narcotic vs non-narcotic, clinical assessment of yeast rash including odor, visible rash, use of fluconazole, ease of dressing application, and amount and type of product used in dressing change.

D. Description, Risks and Justification of Procedures and Data Collection Tools:

A photography release will be distributed and signed by parent at initial visit.

Anursing questionnaire will be completed by nursing staff at each follow up appointment.

Local wound care including cleansing, wound measurement and dressing change will be performed by burn team including nursing staff and occupational and physical therapists. Although punch biopsy with histological analysis is considered the 'gold standard' in assessing burn wound depth, it is invasive and time consuming.¹⁸ Clinical assessment remains the most frequent and rapid method.¹⁸ Due to the time sensitive nature of the proposed trial and in order to avoid delaying wound care and initial dressing application, a 10 point clinical assessment scale has been created, as listed above for use in determining initial burn wound severity. Patient wound depth will be clinically determined by the average of the scores from the provider and the burn nurse.

The wound will also be assessed by the provider and nurse on subsequent visits using the following scoring tool: 1=0% healed, 2=20% healed; 3=40% healed; 4=60% healed; 5=80% healed; 6=100% healed. This will be established by provider and burn nurse examination of the wound. This will be recorded in RedCap.

The overall risk for this study is minimal, with no foreseen adverse reactions. The risk of a silver allergy or adverse reaction to silicone is very rare.

E. Potential Scientific Problems:

Limitations to the proposed study design include varying diagnostic opinions between provider and burn nurse for the determination of superficial vs deep partial thickness burn wounds based on clinical assessment, provider or nurse bias based on dressing preference, and possible uneven trial groups.

F. Data Analysis Plan:

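### The averaged two-rater severity score has no randomisation stratum at 4.5 or 7.5, and no rule says how to place those burns

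*Combined protocol and SAP*

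**What the plan says.** Section IV.C of the combined protocol sets out a 10-point burn severity scale. The provider and the burn nurse each score the patient, and "the severity will be determined based on the average of the 2 numbers". Section IV.D repeats the rule: "Patient wound depth will be clinically determined by the average of the scores from the provider and the burn nurse". Neither section adds rounding, adjudication or a tie-break.

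IV.C then maps scores to three categories. Scores 2, 3 and 4 are partial thickness; "any patient given a 5, 6, or 7 will be placed into the" deep partial thickness group; 8 and 9 are full thickness. Scores 1 and 10 have no category. Randomisation in IV.C uses severity together with age in one paragraph, and is described as balanced by severity in another.

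Two scale points are described as mixtures that include a shallower component. Point 3 is "Second degree, majority superficial partial thickness, minority superficial", while point 2 is superficial partial thickness with no shallower part. Point 6 is "Second degree, majority deep partial thickness, minority superficial partial thickness", while point 5 is deep partial thickness with no shallower part.

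IV.B says "Each injured extremity will serve as a separate data point", whereas IV.C gives one severity number per patient. IV.E lists provider and nurse disagreement on superficial versus deep partial thickness as a limitation. The analysis in IV.F does not mention severity.

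**The concern.** The mean of two whole numbers can be a half-point, but the categories are lists of whole numbers. Half-points within a category's range, such as 3.5 or 6.5, can reasonably be read as belonging to it. Those between categories, 4.5 and 7.5, cannot. The first arises whenever one rater says 4 and the other 5, which is the superficial/deep disagreement that IV.E expects.

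A child at 4.5 or 7.5 cannot be randomised within a severity stratum until someone picks one. The people picking are the clinic staff who treat the child and go on to assess the wound; the protocol describes no blinding, and IV.E itself lists provider or nurse preference for a dressing as a possible bias. At stake is severity balance between the arms. Because IV.F names no severity adjustment, balance at randomisation is the only control for severity that the plan states.

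**Working it through.** The plan gives no figure on this point. Its one design figure, the power statement in IV.F, does not depend on it.

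**Inputs.** From IV.C: whole-number scores, a simple mean, and categories 2–4, 5–7 and 8–9. The categories are read generously, as closed ranges. Read strictly as lists of whole numbers, every half-point mean is unlisted, which is 32 of the 64 ordered pairs on 2 to 9.

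**Step 1: which pairs have no category.** There are 8 scores from 2 to 9, giving 8 × 9 / 2 = 36 unordered pairs (8 × 8 = 64 ordered).
- Mean 4.5 (sum 9): 2/7, 3/6, 4/5.
- Mean 7.5 (sum 15): 6/9, 7/8.

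That is 5 of 36 unordered pairs, or 10 of 64 ordered. Of the 7 one-point splits on 2 to 9, two (4/5 and 7/8) have no category. On the full 1 to 10 scale it is 20 of 100 ordered pairs: 8 at 4.5, 6 at 7.5, and 6 at 1, 1.5, 9.5 or 10.

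**Step 2: how often this could happen.** The documents give no disagreement rate, so a rate *d* of one-point disagreement has to be assumed, with no larger disagreements.
- First score uniform on 2 to 9, second score one point up or down with equal chance where both are possible: a first score of 4, 5, 7 or 8 crosses a boundary half the time, so the share is 4 × (1/8) × (1/2) × *d* = 0.25*d*. For *d* = 10% this is 2.5%; for 40%, 10%; for 50%, 12.5%.
- The seven one-point splits equally likely: the share is (2/7)*d*. For *d* = 10% this is 2.9%; for 20%, 5.7%; for 50%, 14.3%.

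Over *d* = 10% to 50% the range is about 2.5% to 14%, or roughly 2 to 14 of the planned 100 burns.

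**Step 3: does the order of the scale cause the gap?** Swap 2 with 3 and 5 with 6, then repeat Step 1. Ten of 64 ordered pairs still have no category; in the protocol's numbering they are 2/5, 3/7, 4/6, 5/9 and 7/8. The order changes which pairs fall in the gap, not how many.

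**Step 4: does the order matter once the gap is closed?** Use contiguous cut-points: 2 to below 4.5, 4.5 to below 7.5, 7.5 to 9. No pair on 2 to 9 is then unassigned. Putting the scale in depth order changes the category of 4 of 36 pairs:

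| Scores as written | Mean and category as written | Mean and category in depth order |
|---|---|---|
| 2/5 | 3.5, partial | 4.5, deep partial |
| 3/6 | 4.5, deep partial | 3.5, partial |
| 5/9 | 7.0, deep partial | 7.5, full |
| 6/9 | 7.5, full | 7.0, deep partial |

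The first two rows show the inconsistency. By the protocol's descriptions, 3 is milder than 2 and 6 is milder than 5, yet 3/6 lands in the deeper category and 2/5 in the shallower one. All four pairs are disagreements of 3 or 4 points.

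**The case against.** The strongest reply is that this is an omitted detail. A statistician creates the scheme independently, and the RedCap set-up may already map half-points to a stratum. That is possible, but neither IV.C nor IV.D states a mapping; if one exists, writing it down settles the main point. Nor does it help to apply the categories to each rater's own score, since a 4/5 split would then belong to two categories.

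A reader might infer that choosing the stratum biases the allocation. The documents do not establish that. Scores are given before allocation, and a child placed in either adjacent stratum is still validly randomised if staff cannot foresee the next assignment in each. IV.C has the scheme created independently in RedCap but also speaks of a spreadsheet and of a scheme for investigators to follow, so concealment is unclear rather than shown to fail.

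A reader might also infer that the out-of-order scale is what leaves burns without a stratum. It is not: each swapped pair lies inside one category, so burns on which the raters agree, from 2 to 9, are classified the same either way.

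It is also fair to say that pair counts give an unlikely 2/7 split the same weight as a 4/5 split, and that a wrongly placed stratum does not enter the IV.F analysis as written. Both stand. The second means that the harm is loss of balance, not an error in the planned tests.

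**Conclusion.** The concern holds for burns on which the two raters split so that the mean is 4.5 or 7.5. For these, the stated rule gives no stratum, and it fails on a kind of disagreement that the protocol itself expects. The count of 5 in 36 pairs is exact for scores 2 to 9 with the categories read as ranges. The 2.5% to 14% of burns is only an illustration: it rests on assumed one-point disagreement rates of 10% to 50% and an even spread over the scale. Nothing in the documents says which value applies, that disagreement is concentrated at 7/8, or that severity is the strongest predictor of healing; its use as a balancing factor is reason enough to define it.

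The consequence is some loss of severity balance, with a possible opening for selection if the scheme is foreseeable. The depth-order fault is real but secondary: 4 of 36 pairs once cut-points are stated. The point is worth correcting and does not by itself invalidate the design.

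**What to change.** - **Cut-points.** Enter both raw scores in RedCap and have it derive the stratum before allocation, using contiguous cut-points stated in IV.C; for example, means of 2 to below 4.5, 4.5 to below 7.5, and 7.5 to 9. State separately how means below 2 or above 9 are handled, so that open-ended limits do not silently absorb them. Cost: a sentence or two and one calculated field.
- **Order.** Number the scale in depth order before averaging, by exchanging 2 with 3 and 5 with 6. Cost: an edit to the scale in IV.C and to the scoring form.
- **Analysis.** Include the severity category in the log-rank and Cox analysis in IV.F, as a stratum or covariate. Cost: one sentence.
- **Unit.** Reconcile IV.B with IV.C so that each analysed extremity has its own severity score, and state which score sets the stratum when one child has two burns of different severity. Cost: one more pair of scores for each additional burned extremity.

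None of this needs more patients.
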